#### **3.2. Study design**

[figure not shown]
The study is divided in 4 phases.

1. Pretreatment (screening) phase of approximately 28 days. Patients will be evaluated, according to the protocol, before to be enrolled in the study by means of the conventional procedures.
2. Open label non randomized multicenter treatment phase. The investigator will assess patient response to therapy using efficacy measurements and disease response criteria. Patients will be evaluated through this phase for possible toxicities and delays in dosing. Dose modifications will be made as required according to dose modification rules. Patients will be treated with six courses of R-CHOP chemotherapy with a twenty-one day rest period between them. Courses 2,3,4 and 5 will be scheduled with the association of intrathecal chemotherapy with Depocyte®.

Patients with progressive disease at any time will be withdrawn from the study.

3. Consolidation phase. Three weeks after the 6th course of R-CHOP chemotherapy, patients will receive two courses of intermediate-dose Methotrexate therapy every two weeks followed, two weeks later, by scrotal prophylactic radiotherapy or involved field radiotherapy (but can be planned concomitantly to R-CHOP in patients with bilateral disease).
4. Follow-up phase. Patients will be followed for disease progression and survival until the end of the study which is expected to be 36 months after the last patients enrolled into the study completed the treatment. For OS determination information will be required up to 5 years.

The study design is presented in the figure below.

## 4. STUDY POPULATION

### 4.1. General considerations

Patients 18-80 years old are eligible for this clinical trial if they have stage I and II Primary Testicular Lymphoma at diagnosis untreated.

Specific inclusion and exclusion criteria for enrolling subjects in this study are described in the following sections.

## 4.2. Inclusion criteria

Patients must satisfy the following criteria to be enrolled in the study.

1. Patients with primary testicular lymphoma at diagnosis. Histological subtype included into the study is only Diffuse Large B Cell Lymphoma (Attachment 2: WHO classification of lymphoma).
2. Orchiectomy is mandatory, before enrolment of the patient into the study.
3. Orchiectomy should be performed within 2 months before study entry.
4. Age 18-80
5. Untreated patients
6. Ann Arbor Stage IE and IIE. Bilateral testicular involvement at presentation will not be considered Stage IV. These patients may be included into the study and the final Ann Arbor stage (I or II) will be determined by the extent of nodal disease.
7. Bidimensionally measurable or evaluable disease. Patients who have had all disease removed by surgery are eligible.
8. Adequate haematological counts: ANC > 1.0 x 10^9/L and PLTs count > 75 x 10^9/L
9. Cardiac ejection fraction  $\geq$  45% by MUGA scan or echocardiography
10. Non peripheral neuropathy or any active non-neoplastic CNS disease.
11. No other major life-threatening illnesses that may preclude chemotherapy
12. Conjugated bilirubin  $\leq$  2 x ULN.
13. Alkaline phosphatase and transaminases  $\leq$  2 x ULN.
14. Creatinine clearance  $\geq$  45 ml/min.
15. HIV negativity
16. HBV negativity or patients with HBcAb +, HbsAg -, HBsAb+/- with HBV-DNA negative
17. HCV negativity with the exception of patients with no signs of active chronic hepatitis histologically confirmed
18. Life expectancy > 6 months.
19. Performance status < 2 according to ECOG scale.
20. No psychiatric illness that precludes understanding concepts of the trial or signing informed consent
21. Written informed Consent

## 4.3. Exclusion criteria

Potential patients who meet any of the following criteria will be excluded from participating in the study.

1. Has known or suspected hypersensitivity or intolerance to rituximab
2. History of clinically relevant liver or renal insufficiency; significant cardiac, vascular, pulmonary, gastrointestinal, endocrine, neurologic, rheumatologic, hematologic, psychiatric, or metabolic disturbances
3. Uncontrolled diabetes (if receiving antidiabetic agents, subjects must be on a stable dose for at least 3 months before first dose of study drug)
4. Uncontrolled or severe cardiovascular disease including myocardial infarction within 6 months of enrollment, New York Heart Association (NYHA) Class III or IV heart failure (Attachment 5, NYHA Classification of Cardiac Disease), uncontrolled angina, clinically significant pericardial disease, or cardiac amyloidosis
5. History of clinically relevant hypotension

6. CNS involvement (meningeal and/or brain involvement by lymphoma)
7. Evolving malignancy within 3 years with the exception of localized non-melanomatous skin cancer
8. HIV positivity
9. HBV positivity with the exception of patients with HBcAb +, HbsAg -, HBs Ab+- with HBV-DNA negative
10. HCV positivity with the exception of patients with no signs of active chronic hepatitis histologically confirmed
11. Active opportunistic infection
12. Receipt of extensive radiation therapy, systemic chemotherapy, or other antineoplastic therapy
13. Exposure to Rituximab prior study entry
14. Have received an experimental drug or used an experimental medical device within 4 weeks before the planned start of treatment. Concurrent participation in non-treatment studies is allowed, if it will not interfere with participation in this study.
15. Any other co-existing medical or psychological condition that would preclude participation in the study or compromise ability to give informed consent

## 5. REGISTRATION AND STUDY DRUG SUPPLY

Prior to registration the following steps have to be performed:

- check inclusion and exclusion criteria
- obtain informed consent
- complete pre-treatment screening procedures (see study evaluation 9.1.2)
- fill the registration form

**Registration is done by faxing the completed Registration Form**, dated and signed to the IELSG central office:

**The office is open from Monday to Friday 08:00 - 17:00 CET**

A confirmation of registration (**Confirmed Registration / Drug Order Form**) will be faxed by the IELSG to the investigator, and if needed to the coordination office of any national group / intergroup participating to the study.

The same form, which contains the investigator address, to whom Depocyte® must be sent, is also faxed to Mundipharma International Limited, Cambridge, England.

**Mundipharma will then supply the labelled study drug directly to the investigator.**

## 6. DOSAGE AND ADMINISTRATION

### 6.1. Drug administration

The amount (in mg) of RITUXIMAB and of chemotherapeutic agent (CHOP) to be administered will be determined based on body surface area (BSA) using a standard formula provided in Attachment 8, (Suggested Body Surface Area Calculation).

Instructions including calculation of the subject's dose, preparation and handling of the RITUXIMAB infusion are provided in Attachment 4, (Instructions for the Preparation and Handling of RITUXIMAB Injections).

Instructions including preparation and handling of the DEPOCYTE administration, discarding of used study drug supplies, and precautions and care are provided in Attachment 3, (Instructions for the Preparation and Handling of DEPOCYTE Injections).

Study drug will be administered only to eligible subjects under the supervision of the investigator or identified sub-investigator(s).

#### 6.1.1. Treatment schedule and doses

##### Treatment phase

R-CHOP		
Rituximab	375 mg/m 	day 0 or day 1
Cyclophosphamide	750 mg/m 	day 1
Doxorubicin	50 mg/m 	day 1
Vincristine	1.4 mg/m  (2 mg dose max)	day 1
Prednisone	40 mg/m 	day 1-5

##### IT CHEMOTHERAPY

Depocyte® 50 mg on day 0 of cycles 2, 3, 4 and 5 of R-CHOP

R-CHOP courses will be repeated every 3 weeks. The prophylactic intrathecal Depocyte will be given for a total of 4 times, during R-CHOP cycles.

##### Consolidation phase

Begins three weeks after the R-CHOP/IT therapy completion.

##### INTERMEDIATE-DOSE MTX

Methotrexate 1.5 g/m^2

It will be administrated diluted in 500 ml of normal saline solution (NaCl 0.9%). A urine flow  $\geq$  125 ml/hr has to be recorded in the 12 hrs before the MTX administration.

For MTX handling and administration see Attachment 5.

Intermediate-dose Methotrexate courses will be repeated every 14 days for 2 cycles.

All patients will undergo interim restaging procedures after the 3rd course (and before the 4th) of R-CHOP. Clinical response will be re-assessed at the end of planned treatment, one-two month after the completion of the whole therapy, including radiotherapy. Additional imaging studies during the treatment phase will be done only if clinically indicated.

Patients with progressive disease at any time will be withdrawn from the study.

## 6.2. Dose modification and delay

Dose modifications may be made according to any observed toxicity during the previous cycle, as outlined below. Toxicities are to be assessed according to the National Cancer Institute Common Toxicity Criteria for Adverse Events (NCI CTCAE)

version 3.0, 12/12/2003, National Institute of Health (NIH) <http://ctep.cancer.gov/reporting/ctc.html>

### 6.2.1. CHOP dose modification

Patients will start R-CHOP every 21 days if neutrophils  $> 1.0 \times 10^9/L$  and platelets  $> 75 \times 10^9/L$ .

- If neutrophils are  $< 1.5 \times 10^9/L$  and/or platelets  $< 75 \times 10^9/L$ : R-CHOP must be delayed (after 7 days, on day +28)
- If Neutrophils  $\geq 1.5 \times 10^9/L$  and Platelets  $\geq 75 \times 10^9/L$  on Day +28 R-CHOP will be performed with no change in dose

In case of neutropenia Filgrastim or Peg-Filgastrim should be added in the following course of chemotherapy according to "2006 update of recommendations for the use of white blood cell growth factors: an evidence-based clinical practice guideline" (Journal Clinical Oncology 2006 24:3187-3205), and to primary physician judgment in order to avoid delay. Primary prophylaxis of neutropenia with filgastrim or peg-Figastim is allowed in patients over 65 years of age according to the same guidelines.

- Dose modification for sensory neuropathy. No modification as long as neuropathy does not affect function. Any decrease of function (grade 3/4) would lead to dose reduction of vincristine by 50%. If grade 4 toxicity persists after reduction of vincristine by 50%, vincristine may be eliminated from subsequent cycles.
- Prednisone dose may be decreased by 50% or discontinued if patients have increase in serum glucose to  $> 300 \text{ mg/dl}$ , or other psychological disturbances such as psychosis or anxiety attacks.

Just patients who have achieved PR/CR after three cycles of CHOP will continue therapy. All other patients will be removed from the study and will be considered for other possible therapies according to the local policy.

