# 1. INTRODUCTION

## 1.1. Background

### 1.1.1. Primary testicular lymphoma background

PTL is a rare disease that represents 1% to 2% of all non-Hodgkin's lymphomas, with an estimated incidence of 0.26/100,000 per year. 1 PTLs account for no more than 5% of all testicular malignancies, however they represent the most frequent testicular cancer in men older than 50 years of age. 2 PTL is a typically disease of elderly, 85% of PTLs are diagnosed in men over 60 years of age. 3 Histologically, 90% or more of PTLs are of diffuse large-cell type (DLBCL) with B cell phenotype.

PTL has a propensity to disseminate systematically to several extranodal sites including the contralateral testis, central nervous system (CNS 6% - 16%), skin (0% - 35%), Waldeyer's ring (5%), lung, pleura and soft tissue. Mainly, the portion of patients showing CNS involvement at diagnosis, 2% to 16%, is higher than in nodal lymphomas.3,6,7

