## 8. CONCOMITANT THERAPY

During treatment are recommended as concomitant therapy:

- Pre-phase therapy is recommended in older patients ( $>65$  years) with PDN 100 mg/die for 10 days and VCR 1.5 mg total dose
- G-CSF or Peg-Filgrastim as primary prophylaxis for the prevention of febrile neutropenia in older ( $>65$  years) patients in according to 2006 Update of Recommendations for the use of white blood cell growth factors (Smith TJ, Khatcheressian J, Lyman GH, et al. 2006 Update of Recommendation for use of white blood cell growth factors: an evidenced-based clinical practice guideline. J Clin Oncol 2006; 24: 3187-3205)
- Cotrimoxazole BACTRIM 3 tablets/week (or 1 x 2/day for two days/week) or Pentamidine aerosol every 15 days in patients with Bactrim allergy or in patients with G6PD deficiency throughout the treatment and consolidation phase
- In patients with Ab antiHBcAg +, Ab antiHBsAg +/- prophylaxis against hepatitis B reactivation with Lamivudine 100 mg/die from the start of the treatment to one year after the end of the treatment

All concomitant medications for medical conditions other than B-NHL are permitted, as clinically indicated.

All supportive therapies other than anti-cancer treatment needed for the management of patients enrolled in this study are permitted.

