## 8.1. Permitted therapy

The following medications and support therapies that may be used if needed during this study:

- Antiviral prophylaxis with acyclovir 800-1200 mg at day since the beginning of therapy is strongly recommended in patients with herpes virus infection reactivation Additional prophylaxis with levofloxacin or ciprofloxacin will be administered in case of neutropenia  $<1.0 \times 10^9/l$ .
- G-CSF or Peg-Filgastrim is allowed and will be given according to primary physician decision in presence of neutropenia  $< 1.0 \times 10^9/l$ .
- Platelets and red blood cell transfusion are allowed, if needed with filtered and irradiated products in case of Hb  $< 8 \text{ g/dL}$  or Plts  $< 10 \times 10^9/l$ .
- Erythropoietin therapy is allowed according to ASH/ASCO guidelines
- Immunoglobulin assay is advisable once a month during the therapy with immunoglobulin replacement in case of IgG level  $< 0.3-0.5 \text{ gr/dl}$  and frequent infectious events.
- Laxatives and other prebiotics and probiotics are recommended to prevent constipation and should be administered according to standard practice
- Antiemetic agents
- Premedication for rituximab infusion with paracetamol and diphenhydramine is mandatory before each infusion of rituximab, because it may reduce infusion reactions.
- Use of corticosteroids is allowed in emergency or as pre-medication for rituximab infusion

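### Section 6.2.1 gives opposite instructions on day 21 when neutrophils are between 1.0 and 1.5 and platelets exceed 75 x10^9/L: one line starts R-CHOP, the next delays it to day +28

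*Combined protocol and SAP*

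**What the plan says.** Three consecutive statements in section 6.2.1 govern when the next R-CHOP cycle is given (counts in x10^9/L).

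- **Start line.** "Patients will start R-CHOP every 21 days if neutrophils" exceed 1.0 and platelets exceed 75.
- **Delay line.** If neutrophils are below 1.5, or platelets below 75, or both, "R-CHOP must be delayed (after 7 days, on day +28").
- **Day +28 line.** If neutrophils are at least 1.5 and platelets at least 75, "on Day +28 R-CHOP will be performed with no change in dose".

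The value 1.0 also appears at entry, in inclusion criterion 8 of section 4.2: "Adequate haematological counts: ANC > 1.0 x 10"^9/L.

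Growth factor support is covered in three places. Section 6.2.1 states: "In case of neutropenia Filgrastim or Peg-Filgastrim should be added in the following course of chemotherapy", with reference to a published guideline and the physician's judgement, the aim being to avoid delay. Section 8 recommends "G-CSF or Peg-Filgrastim as primary prophylaxis for the prevention of febrile neutropenia in older" patients, meaning those above 65 years. Section 8.1 reads "G-CSF or Peg-Filgastrim is allowed and will be given according to primary physician decision in presence of neutropenia" below 1.0.

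Section 3.2 says that doses will be modified according to the protocol's rules and that patients will be evaluated for toxicity and for delays in dosing. Section 2.1 makes safety and feasibility the primary objective.

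**The concern.** The start line and the delay line use different neutrophil cut-offs, 1.0 and 1.5, and each is written as an instruction. Between the two values both conditions are met and the actions are opposite. Two sites following the protocol to the letter could treat the same patient a week apart.

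That matters for the patient's dose intensity. It also matters for what the trial reports: a delay might reflect which line a site chose to follow rather than how well the regimen was tolerated. In cycles 2 to 5 the intrathecal liposomal cytarabine is given on day 0 of the cycle (section 6.1.1), so a delay moves that dose too.

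**Working it through.** The plan gives no figure to reproduce here, so the check is logical, followed by simple schedule arithmetic.

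**Step 1: code the two day-21 lines.** Start = (neutrophils > 1.0 and platelets > 75). Delay = (neutrophils < 1.5 or platelets < 75).

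| Neutrophils | Platelets 74 | Platelets 75 | Platelets 76 or 100 |
|---|---|---|---|
| 0.9, 1.0 | delay | delay | delay |
| 1.01, 1.2, 1.49 | delay | delay | **start and delay** |
| 1.5, 1.6 | delay | **neither** | start |

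The conflict region is exactly 1.0 < neutrophils < 1.5 with platelets > 75. There is also a boundary gap: platelets of exactly 75 with neutrophils of at least 1.5 satisfy neither line.

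**Step 2: look for a reading that removes the conflict.**

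- The start line cannot be a cycle 1 rule only, because it refers to starting every 21 days.
- The delay line is mandatory in its wording, so it is not an option that sites may decline.
- A misprint cannot be resolved from context. The value 1.0 is supported by inclusion criterion 8, and 1.5 by the day +28 line.
- No other section sets an order of precedence.

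**Step 3: the day +28 line.** It covers recovered counts only. For a patient still at 1.2 on day +28 there is no recheck interval, dose reduction or maximum delay. Section 10.2 offers only investigator discretion on safety grounds, or discontinuation for toxicity of grade 3 or worse lasting more than 2 weeks.

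**Step 4: size per occurrence.** Inputs are the 21-day interval (section 6.1.1), the 7-day delay (section 6.2.1) and the schedule in section 3.2 and Attachment 9.

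- Dose intensity of one delayed interval: 21/28 = 0.75.
- Cycle 6 as planned: 5 x 21 = day 105, which matches Attachment 9. After one delay: 105 + 7 = day 112.
- Average intensity over the five intervals: 105/112 = 0.9375, about 94%.
- Methotrexate: 112 + 21 = day 133 and 133 + 14 = day 147, against the planned days 126 and 140.

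These figures assume that counts recover to at least 1.5 and 75 by day +28. Without recovery no restart day is defined, so no upper limit on the delay can be given.

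**Step 5: number of decisions.** 35 patients x 5 starts (cycles 2 to 6) = 175. This is a ceiling, since section 9.1.4 withdraws patients with stable or progressive disease after cycle 3. The share falling in the disputed band is not in the documents. As an assumption only:

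| Assumed share | Decisions affected |
|---|---|
| 2% | 0.02 x 175 = 3.5, about 4 |
| 5% | 0.05 x 175 = 8.75, about 9 |
| 10% | 0.10 x 175 = 17.5, about 18 |

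**The case against.** The strongest reply is that the ambiguity is smaller in practice than on paper. Two of the three lines use 1.5, and only the delay line carries mandatory wording, so a cautious site would probably delay. That is a fair inference, but the protocol does not state it, and a site treating on day 21 would be following the start line as written.

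Growth factor use also reduces the problem. Section 1.1.1 notes that "85% of PTLs are diagnosed in men over 60 years of age", so the group above 65 who are recommended primary prophylaxis may be large, although its share is not given. Section 6.2.1 also directs growth factor support in the following course specifically to avoid delay. This should lower the frequency, but it does not say what to do when a count of 1.2 is found on day 21. Section 6.2.1 sets no count for neutropenia, pointing instead to a guideline and clinical judgement, and the section 8.1 trigger lies below the disputed band.

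On non-recovery, it can be argued that the delay line still applies on day +28, so the natural reading is to keep waiting. That is reasonable; what is missing is when to recheck and when to stop. The boundary at exactly 75 platelets is a drafting slip of very small consequence.

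Finally, the assumed shares in the working are not evidence. That is right: they show scale only, and the conclusion does not depend on them.

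**Conclusion.** The contradiction holds. With neutrophils strictly between 1.0 and 1.5 and platelets above 75, section 6.2.1 both starts and delays the cycle, and no other text settles it. It should be fixed.

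The consequence is one week per occurrence, at a frequency the documents do not allow us to estimate. It bears on dosing and on how delays are to be interpreted for the feasibility objective. It goes no further than that: no delay-based endpoint or feasibility threshold is defined, section 9.4 names only grade 3-4 haematological toxicity, and the sample size and error rates do not depend on it. The 21- versus 28-day conflict does not itself create an event-free survival event. The separate lack of a non-recovery rule could do so only indirectly, if it led to treatment being stopped, because section 9.3.1 counts discontinuation for any reason as an event.

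**What to change.** Use one neutrophil threshold throughout section 6.2.1. The clinical choice is the sponsor's; either option below leaves no overlap and no gap.

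| Line | Option A (1.5) | Option B (1.0) |
|---|---|---|
| Start, day 21 | neutrophils >= 1.5 and platelets >= 75 | neutrophils > 1.0 and platelets >= 75 |
| Delay | neutrophils < 1.5 and/or platelets < 75 | neutrophils <= 1.0 and/or platelets < 75 |
| Restart, day +28 | neutrophils >= 1.5 and platelets >= 75 | neutrophils > 1.0 and platelets >= 75 |

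Option A changes only the start line, and should be limited to cycles 2 to 6 so that it does not conflict with the entry criterion. Its cost is some extra one-week delays. Option B fits if the entry cut-off was the intended treatment threshold.

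In the same amendment, state what happens when counts have not recovered by day +28: the recheck interval, and when to reduce the dose or stop.

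One separate clarification could be made at the same time. Section 6.2.1 allows treatment to continue without vincristine for persistent grade 4 neuropathy, while section 10.2 discontinues for any toxicity of grade 3 or worse lasting more than 2 weeks. Section 10.2 should say whether toxicities managed under 6.2.1 are exempt.

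The threshold correction takes two or three sentences and a site notice. The non-recovery rule adds a little text and needs a clinical decision. Neither changes the sample size or the analysis.

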### 6.2.2. Rituximab dose modification

Rituximab administration and dose modification must follow labeling instructions and guidelines. Please refer to the approved product label for instructions.

Patients who develop severe infusion reactions should have rituximab infusion discontinued and supportive care measures as medically indicated (e.g. fluids, vasopressors, oxygen, bronchodilators, acetaminophen, etc.). In most cases, the infusion can be resumed at 50% reduction rate (e.g. from 100 mg/hr to 50 mg/hr) when symptoms have completely resolved. Patients requiring close monitoring during first and all subsequent infusions include those with pre-existing cardiac and pulmonary conditions, those with prior clinically significant cardiopulmonary adverse events, and those with high numbers of circulating malignant cells ( $> 25 \times 10^9/l$ ) with or without evidence of high tumor burden.

